Title of the Study: CCRC: Randomized trial of L-arginine in severe asthma patients grouped by exhaled nitric oxide levels (NCT #01841281)

Principal Investigator: [name], MAS

Updated: December 15, 2019

Last IRB Approval Date: July 16, 2018

PROTOCOL

PURPOSE AND PROCEDURES:

1. Describe the study format (pilot, phase I, phase II, or III) and whether it is single or multi-center; industry-sponsored or investigator initiated; and the funding source.

This is an investigator-initiated, early phase II study funded by NHLBI.

2. Describe the specific aims of the study, research methods and procedures.

We hypothesize that a subset of adult severe asthma patients will respond to supplemental L-arginine and derive clinical benefit from the addition of this therapy to standard-of-care medications. We hypothesize that these patients will have lower exhaled NO concentrations (<20 ppb) than -non-responders. The aim is:

1. To test the hypothesis that adult severe asthma subjects with exhaled breath NO concentrations <20 ppb will have fewer American Thoracic Society (ATS)-defined asthma exacerbations over 3 months when treated with L-arginine compared to subjects with FeNO > 25.

The major impact of this study will be to identify the adult severe asthma cohort that will benefit from supplemental L-arginine therapy to define the underlying mechanisms of arginine benefit in asthma. This follows our initial 20 subject trial of L-arginine in asthma subjects ([name] et al., Pharmaceuticals 2011) that was designed to determine how L-arginine was metabolized (by testing serum markers) and whether certain participants had clinical benefit.

To do this, we will recruit a total of 50 ATS-defined asthmatic subjects with ≥ 2 asthma exacerbations in past two months and enroll them in a randomized, blinded, placebo-controlled, cross-over designed trial of L-arginine and placebo. We will compare 25 subjects with -low FeNO <20 with 25 subjects that have -high FeNO > 25 ppb.

Study Design:

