The primary endpoint was the total number of "moderate" exacerbations during the 12-week interventional period, as defined by recent the ATS/ERS 2009 statement [2]. A moderate asthma exacerbation is defined as any of the following: 1) a drop in am PEF>30% from baseline on two consecutive days, 2) need for initiation of oral steroids or an increased dose of inhaled corticoid steroid on any two consecutive days, 3) doubling of short-acting β -agonist use (e.g. number of puffs of albuterol)/ day for 2 consecutive days [3-5]. The secondary clinical endpoints were recorded at each of the six study visits, these included: 1) asthma control test score, 2) FEV1 (liters), 3) FVC (liters), 4) FEV1/FVC (%), and 5) Weight. The secondary biological endpoints including FeNO and untargeted metabolites.

Metabolites measurement

Longitudinal plasma metabolite levels were measured by hydrophilic interaction liquid chromatography (HILIC) in both positive and negative modes and gas chromatography (GC) mode. The peak intensity was measured for the compounds and were annotated to specific known metabolites. Relative standard deviation (RSD) for each compound found in more than one mode in quality control samples were calculated and the intensities of compound with lowest RSD was chosen for the downstream analysis.

Clinical trial analysis

For the sample size calculation, we used a conservative power estimate based on t-test analysis of 2x2 cross-over design [6]. For a sample size of 50 people, we would have 95% power to detect a 0.6 standard deviation change in the mean lung function at $\alpha = 0.025$ and accounting for 10% attrition rate. Improvements of this magnitude are consistent with those reported in recent crossover trials in asthma with either FEV1 [7], symptoms scores [8], or AM PEF [9] as outcomes. Statistical analyses for the clinical trials were performed using SAS University Edition (SAS Institute Inc., Cary, NC, USA.) and R (public access). Data were analyzed on an intention-to-treat basis and the significant level was defined by p value less than 0.05. A generalized linear mixed model was used for analysis accounting for correlated repeated measurements which enable us to account for expected missing data points [10]. This model considered differences in baseline levels of function, by allowing for person-specific random effects (random intercepts). The distribution of exacerbation events was assumed to be a Poisson distribution. For

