the primary hypothesis, we included an indicator in the model that allows for the subjects to be on active treatment. We first examined the carryover and period effect then tested for the treatment effect and examined the interaction term between treatment and FeNO. For secondary clinical outcomes, we performed the same analysis except we used linear mixed effect for the continuous endpoints.

Identify baseline metabolites as predictors for treatment response

We further defined the treatment response by reducing exacerbation events by 33% during L-arginine treatment. The individual event reduction was calculated by (events during treatment period minus events during placebo period)/events during placebo period. Subjects with zero event at baseline or did not complete both treatment and placebo phase were excluded. The baseline metabolomic profiling (first visit) was used for the downstream analysis. Partial Least Square-Discriminant analysis (PLS-DA) and hierarchical cluster analysis (using Euclidean as similarity measure and Ward's linkage as clustering algorithm) were performed using MetaboAnalyst 4.0 [11]. to identify the predictive metabolites. Clinical characteristics were compared between treatment response versus non-response groups using t-test (continuous characteristics) or Fisher's exact test (categorical characteristics with small sample sizes).

Longitudinal metabolomic profiling analysis

A linear mixed model was used to test the association between the longitudinal metabolite intensities and the clinical outcomes including FeNO at each visit. Metabolites pattern change between two biological conditions including 1) treatment vs. placebo, 2) high vs. low FeNO groups during treatment period, 3) treatment response vs. non-response groups during treatment period were tested using the method of multivariate empirical Bayes (MEBA) time-series analysis [12] built in the MetaboAnalyst 4.0. Hotelling-T2 statistics were used to rank the metabolites with different temporal profiles between two biological conditions under the study.

References

- [name], Last M., Bratt J.M., Kwan V.W., O'Roark E., Linderholm A. L-Arginine Supplementation and Metabolism in Asthma. *Pharmaceuticals* 2011, 4, 187-201.

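### Predictive baseline metabolites are to be named from an in-sample PLS-DA with no validation step, so high apparent accuracy would be expected even from pure noise

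*Combined protocol and SAP*

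**What the plan says.** The step is in the Combined protocol and SAP, under Statistical Analysis Methods, in the subsection on baseline metabolites as predictors of treatment response.

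- **Label.** "We further defined the treatment response by reducing exacerbation events by 33% during L-arginine treatment". Non-completers and zero-event subjects are left out.
- **Predictors.** "The baseline metabolomic profiling (first visit) was used for the downstream analysis".
- **Method and purpose.** "Partial Least Square-Discriminant analysis (PLS-DA) and hierarchical cluster analysis" are run in MetaboAnalyst 4.0 "to identify the predictive metabolites".
- **Panel.** The Outcomes subsection says: "The secondary biological endpoints including FeNO and untargeted metabolites". The Metabolites measurement subsection names the platforms as "hydrophilic interaction liquid chromatography (HILIC) in both positive and negative modes and gas chromatography (GC) mode". Peaks are annotated to known compounds, and a compound seen in several modes is kept once, from the mode with the lowest relative standard deviation. The size of the resulting panel is not given.
- **Subjects.** In the protocol's description of aims, "we will recruit a total of 50 ATS-defined asthmatic subjects". The sample-size paragraph is described as "accounting for 10% attrition rate".

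For this step the document mentions no cross-validation, label permutation, hold-out or external sample, Q2, rule for the number of components, importance cut-off or multiplicity control. The general 0.05 significance level is not tied to any PLS-DA quantity.

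**The concern.** PLS-DA is supervised: it builds its components from the response labels. When the panel is large relative to the number of subjects, chance associations are enough to build a score that divides responders from non-responders in the data used to fit it. In-sample separation therefore says little about prediction. Nothing else in the plan provides the missing check:

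- The hierarchical clustering uses the same subjects and the same profiles.
- The t-tests and Fisher tests compare clinical characteristics, not metabolites.
- The later time-series (MEBA) analysis uses the same subjects, with the same response label as one of its contrasts.

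At stake is the claim that certain metabolites predict who responds. If that claim rests on in-sample fit, a reader cannot tell a real signature from an artefact.

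**Working it through.** **Stated figures.** The plan gives no figure for this step. The nearest is the 95% power. Taking 50 × 0.9 = 45 completers, 45 − 2 = 43 degrees of freedom, two-sided alpha 0.025, and 0.6 read as SDs of the within-subject difference, the noncentrality is 0.6 × √45 = 4.02 and the power is 0.952. This reproduces the figure and supports 45 as the planned number of completers. It has no other bearing here.

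**Inputs.**
- From the documents: n is at most about 45, and lower by an unknown amount after zero-event exclusions; three measurement modes; two classes.
- Assumed, because not stated: number of metabolites p, number of components, responder share (50:50 unless noted), and correlation between metabolites.

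**Analytic check, one component.** The first PLS score is proportional to XX′y. With y coded ±½ and noise predictors, each subject's own label contributes about p/2, and the other subjects contribute noise with SD about √(np)/2. In-sample accuracy is therefore about Φ(√(p/n)). For blocks of 10 metabolites with correlation 0.5, the noise variance rises by 1 + 9 × 0.5² = 3.25, giving Φ(√(p/(3.25n))). At n = 45:

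| p | Independent: formula | Simulated | Correlated: formula | Simulated |
|---|---|---|---|---|
| 50 | Φ(1.05) = 0.85 | 0.863 | Φ(0.58) = 0.72 | 0.740 |
| 100 | Φ(1.49) = 0.93 | 0.936 | Φ(0.83) = 0.80 | 0.818 |
| 200 | Φ(2.11) = 0.98 | 0.984 | Φ(1.17) = 0.88 | 0.894 |

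Apparent accuracy is thus governed by p/n, with p discounted for correlation. It rises smoothly; there is no jump at p = n.

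**Simulation, pure noise.** PLS-DA on autoscaled data, 60 runs per cell, 10-fold cross-validation on 20 of them. Perfect separation means in-sample AUC = 1. Q2 = 1 − (squared error of held-out predictions)/(total sum of squares). At n = 45, each cell shows independent / correlated:

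| p | Components | In-sample accuracy | Share perfectly separated | Cross-validated accuracy | Q2 |
|---|---|---|---|---|---|
| 50 | 2 | 0.938 / 0.865 | 0.12 / 0.00 | 0.460 / 0.490 | −0.78 / −0.53 |
| 100 | 2 | 0.996 / 0.940 | 0.98 / 0.17 | 0.489 / 0.498 | −0.43 / −0.61 |
| 200 | 1 | 0.984 / 0.894 | 0.87 / 0.02 | 0.478 / 0.457 | −0.21 / −0.38 |
| 200 | 2 | 1.000 / 0.992 | 1.00 / 0.85 | 0.498 / 0.494 | −0.25 / −0.47 |
| 200 | 3 | 1.000 / 1.000 | 1.00 / 1.00 | 0.478 / 0.503 | −0.30 / −0.49 |
| 500 | 2 | 1.000 / 1.000 | 1.00 / 1.00 | 0.453 / 0.478 | −0.19 / −0.29 |

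Fewer subjects make it worse: at n = 20, p = 50, two components, correlated, in-sample accuracy is 0.967 and 0.73 of runs separate perfectly, against 0.865 and 0.00 at n = 45.

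**Range.** A second noise simulation with 5-fold cross-validation (n = 20-45, p = 50-400, 1-3 components, independent or correlated) gave in-sample accuracy of 0.75-1.00 and cross-validated accuracy of 0.40-0.52 in every cell. A third, with two components and responder shares of 50% or 33%, gave mean in-sample AUC of 0.957-1.000 against cross-validated AUC of 0.38-0.50, so the result does not depend on balanced classes.

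**Metabolite level.** The plan states no importance cut-off. If VIP > 1 were used, about 66 to 74 of 200 pure-noise metabolites would pass with two or more components (66/200 = 0.33; 74/200 = 0.37).

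**The case against.** Four stronger readings are tempting, and the documents support none of them.

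1. *The panel is larger than the sample.* A reader might infer this from untargeted profiling in three modes. It is plausible, but annotation and removal of duplicates shrink the panel, and its size is not stated. It must remain an assumption.
2. *PLS-DA always separates the classes perfectly once p exceeds n.* It does not. At n = 45 and p = 50 with two components, perfect separation occurred in 12% of independent and none of the correlated noise sets. With p = 200, one component and correlated metabolites it occurred in 2%.
3. *The trial's main purpose is undermined.* The protocol's statement of major impact follows an aim that defines the cohort by FeNO, which is tested by the treatment-by-FeNO interaction. Metabolites are secondary biological endpoints. A follow-on Phase III study is mentioned, but nothing says that a metabolite signature would select its patients.
4. *The plan must return false predictors.* It has no selection rule, so it is silent on what would be named. Its defect is that it contains no step able to show that nothing predicts.

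It can also be said that validation details may be left to the named software. Naming a program does not commit the analysts to a procedure or to a criterion for claiming prediction. Points 1 to 4 limit the size and reach of the concern. They do not remove it: cross-validated accuracy was at chance throughout, while in-sample accuracy was well above it.

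**Conclusion.** The concern holds in a limited form. The SAP would call baseline metabolites predictive on the strength of a supervised fit, and a clustering of the same data, with no out-of-sample check, in at most about 45 subjects. Under the assumed ranges (50-400 metabolites, 1-3 components, 20-45 subjects, equal classes), noise alone gives in-sample accuracy of about 0.75-1.00 against about 0.40-0.52 cross-validated. Perfect or near-perfect separation is the expected result only from roughly 200 metabolites and two components upwards; below that it ranges from rare to common. The exact size depends on panel size, number of components and correlation, none of which the documents give. The primary exacerbation analysis and the FeNO interaction are unaffected. Because the claim is secondary and the remedy cheap, the plan should be changed, but this is not a fatal defect.

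**What to change.** Amend the subsection on baseline predictors as follows.

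- State the number of metabolites and subjects entering the model, and choose the number of components by a pre-specified cross-validation rule.
- Report only cross-validated accuracy and Q2, with scaling and any filtering redone inside each fold.
- Add a label-permutation test of the whole model (for example 1000 permutations), repeating the full procedure, component choice included, each time. Claim that the profile predicts response only if p < 0.05.
- Name individual metabolites only with metabolite-level support, such as false-discovery-rate control or selection stability across folds. The model-level test is not enough: in a simulation with n = 40, p = 200 and 5 true metabolites, about 50 of the 195 noise metabolites still had VIP > 1 (an assumed cut-off) when the permutation test passed.
- Present the clustering as descriptive, and label all results of this step exploratory pending confirmation in independent subjects.

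The cost is a few lines in the SAP and minor computing. No new data are needed, since the first-visit profiles can be re-analysed. The real price is that possibly no metabolite will qualify.

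### No multiplicity control is stated for the mixed models of untargeted metabolites, a named secondary endpoint; at p<0.05 about 5 false associations per 100 metabolites per outcome are expected when none is real

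*Combined protocol and SAP*

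**What the plan says.** All places are under Statistical Analysis Methods.

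- *Outcomes* gives the metabolites formal status: "The secondary biological endpoints including FeNO and untargeted metabolites". The visit-level secondary clinical endpoints listed just before are "1) asthma control test score, 2) FEV1 (liters), 3) FVC (liters), 4) FEV1/FVC (%), and 5) Weight".
- *Metabolites measurement* describes an assay by "hydrophilic interaction liquid chromatography (HILIC) in both positive and negative modes and gas chromatography (GC) mode". Of the compounds it says: "The peak intensity was measured for the compounds and were annotated to specific known metabolites". A compound seen in more than one mode is kept once, in the version with the lowest relative standard deviation. The number of compounds is not given.
- *Clinical trial analysis* holds the only analysis threshold: "the significant level was defined by p value less than 0.05".
- *Longitudinal metabolomic profiling analysis* sets out the mixed models: "A linear mixed model was used to test the association between the longitudinal metabolite intensities and the clinical outcomes including FeNO at each visit". It then describes MEBA comparisons for three contrasts, "1) treatment vs. placebo, 2) high vs. low FeNO groups during treatment period, 3) treatment response vs. non-response groups during treatment period", and says of their output: "Hotelling-T2 statistics were used to rank the metabolites with different temporal profiles between two biological conditions under the study".

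No section states a false discovery rate, a q-value, a Bonferroni correction or any other adjustment for the metabolites. No section labels the metabolite work exploratory.

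**The concern.** An untargeted assay produces many metabolites, and each is to be tested against more than one outcome. A per-test rule of 0.05 lets through 5% of all true null tests, so the number of false calls grows in step with the number of tests. With only 50 subjects there is little scope to check such calls within the trial.

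The protocol presents an explanation of how arginine helps as part of the study's main value, and metabolite associations are the natural evidence for it. Because metabolites are a named secondary endpoint, a reader of the report would take a significant metabolite at face value. The plan gives no rule that would justify doing so.

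**Working it through.** **The plan's own figure.** The plan gives no count of metabolite tests and no error rate for them, so there is nothing to reproduce on this point. Its one checkable figure, 95% power in the sample size statement, reproduces at 95.2% (45 evaluable subjects, two-sided 0.025, 0.6 read as a multiple of the SD of the within-subject difference). It has no bearing here.

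**Inputs.**
- Per-test level: α = 0.05, from *Clinical trial analysis*. Its use for metabolites is inferred.
- Number of outcomes K: not stated for this analysis. Five visit-level clinical endpoints plus FeNO give 6. Adding the exacerbation count gives 7.
- Number of metabolites M: not given. Assumed 50 to 500.

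**Expected false associations when none is real** = M × K × α, taking each test to have its nominal size. For 100 metabolites and one outcome: 100 × 1 × 0.05 = 5. For 100 metabolites and six outcomes: 100 × 6 × 0.05 = 30.

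| M (assumed) | K = 1 | K = 6 | K = 7 |
|---|---|---|---|
| 50 | 2.5 | 15 | 17.5 |
| 100 | 5 | 30 | 35 |
| 300 | 15 | 90 | 105 |
| 500 | 25 | 150 | 175 |

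At a level of 0.025 every entry halves. Correlation among metabolites or outcomes leaves these expected counts unchanged but widens their spread. If some associations are real, the count falls in proportion to the share of true nulls.

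**Chance of at least one false association**, for independent tests = 1 − 0.95^(M × K). With 50 tests this is 1 − 0.95^50 = 92%. From 300 tests it is effectively 100%.

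**With control over the whole metabolite-by-outcome family.** Two cases were simulated, with 2,000 runs each, independent tests and no real association:
- M = 100, K = 6 (600 tests): unadjusted, 30.1 false calls on average. Benjamini-Hochberg at 5%: 0.055 on average, with a 5.0% chance of any.
- M = 300, K = 6 (1,800 tests): unadjusted, 90.0. Benjamini-Hochberg: 0.056, with a 5.1% chance of any.

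For comparison, the Bonferroni thresholds would be 0.05/600 = 8.3 × 10⁻⁵ and 0.05/1,800 = 2.8 × 10⁻⁵.

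**Control within each outcome separately.** With six independent outcomes and no real association, the chance of any false discovery is 1 − 0.95^6 = 26%. The choice of family therefore matters.

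**The case against.** The strongest reply is that the plan never says metabolites are judged at p<0.05. The threshold stands in a paragraph about the clinical trial analyses. The metabolomic sections have their own headings and no threshold, and the clinical analysis is explicitly extended only to the secondary clinical outcomes. This stands: the 0.05 is an inference. It does not remove the gap, since the alternative reading is that a tested secondary endpoint has no decision rule at all, and the same change repairs that.

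It can also be said that this is early phase II work with one numbered aim, on exacerbations. The protocol says it is not meant to support a new indication and foresees a later phase III trial. The mixed models relate metabolites to outcomes and do not compare treatments, so no efficacy conclusion depends on them. That limits the weight of the point. But the plan does not call the metabolite work exploratory; it calls it a secondary endpoint.

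Three stronger readings are tempting and are not supported:
- **That dozens of false associations must occur.** Reaching 24 needs 24/0.05 = 480 tests, which is 80 metabolites with six outcomes or 480 with one. Neither count is given, and restriction to annotated, de-duplicated compounds lowers M by an unknown amount.
- **That most reported associations would be false.** This depends on the share of real associations and on power, and the documents give neither. With 300 metabolites, one outcome, 5% real and 50% power, there are 15 × 0.5 = 7.5 true and 285 × 0.05 = 14.25 false calls, so 66% are false. With 10% real and 80% power, there are 24 true and 13.5 false, so 36% are false.
- **That the treatment contrasts on metabolites are equally affected.** The MEBA passage does use the word tested, but the only output it describes is a ranking, with no p-value cut-off to count false positives against.

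**Conclusion.** The point holds for the metabolite mixed models. A named secondary endpoint is tested against several outcomes, no error-rate control is stated, and the plan's only significance rule is an unadjusted p<0.05. If that rule is used, about 5 false associations per 100 metabolites per outcome are expected when none is real, or about 15 to 150 for 50 to 500 metabolites and six outcomes.

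The per-100 figure rests on the 0.05 carrying over and on no association being real. The 15 to 150 range also rests on the assumed metabolite and outcome counts. The primary endpoint and the treatment comparisons on clinical outcomes are untouched. The change should be made because it alters which metabolites are reported as associated, and it costs almost nothing.

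**What to change.** In *Longitudinal metabolomic profiling analysis*, for the mixed models:

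1. State the number of metabolites analysed and list the outcomes, so that the number of tests is known.
2. Define the family as all metabolite-by-outcome tests and apply the Benjamini-Hochberg procedure at a 5% false discovery rate across it, not outcome by outcome.
3. Report q-values together with the number of tests.
4. State that p<0.05 applies only to the clinical endpoints, and label any unadjusted metabolite result hypothesis-generating.

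The cost is a few sentences in the plan and a short step in the code. The q-values can be computed from existing p-values without new data. The downside is that fewer metabolites will be called associated. The section is written in the past tense, so if the models have already been run, the report should present the adjustment as added afterwards and not as prespecified.

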- *Exhaled Breath Condensate (EBC) Collection:* Collections of EBC from each participant will occur immediately after collection of the exhaled breath samples. Participants will breathe into a chilled collection tube for 10 minutes as recommended in the 2005 ATS/ERS statement. Collection tubes will be purchased from Respiratory Research (Charlottesville, VA), a commercial entity that has received FDA approval for measuring EBC pH in subjects with cough. Immediately after collection, the tubes will be frozen on dry ice for transport to [name] lab. Total time of sample collection should be 10 minutes. Breath samples will undergo chemical analysis at [name] laboratory. Volatiles in breath samples will be concentrated using Solid Phase Microextraction (SPME). Analyte compounds will then be loaded on a chromatographic column for a nominal pre-separation and will be detected with a differential mobility spectrometer, according to protocols previously developed in [name] lab.
- *Blood draw* 16 cc of blood will be drawn at each visit. Serum will be collected for cytokine profiling and NOx measurements and L-arginine metabolites. Whole blood will be processed for genotyping.

- *Office Spirometry will be performed with portable office spirometer (Spriolab II).*
- *Physical examination and symptom questionnaire*

Brief Study outline: 1 screening visit and 4 study visits

- Screening Visit
- Explanation of protocol
 - Informed consent
 - History and physical examination
 - Two exhaled NO measurements (to determine if subjects > or < 25 ppb)
- Study Day 1
- History and physical examination (brief) to verify stable clinical status
 - Blood collection #1
 - Spirometry #1
 - Exhaled NO measurement #1
 - Sputum collection #1
-
- Respiratory symptom questionnaire #1
 - Start symptom and peak flow diary
 - Start oral L-arginine or placebo
- Study Day 80
- Updated clinical history
 - Blood collection #2
 - Spirometry #2
 - Exhaled NO measurement #2
 - Sputum collection #2
 - Respiratory symptom questionnaire #2
- Study Day 110
- Updated clinical history
 - Blood collection #3
 - Spirometry #3
 - Exhaled NO measurement #3
 - Sputum collection #3
 - Respiratory symptom questionnaire #3
- Study Day 190
- History and full physical examination
 - Blood collection #4
 - Spirometry #4
 - Exhaled NO measurement #4
 - Sputum collection #4
 - Respiratory symptom questionnaire #4
 - Stop oral L-arginine or placebo

5. If blood samples will be collected, identify in what manner:

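### The responder versus non-responder metabolite contrast uses blood from the same L-arginine period whose exacerbations partly define the groups, so effects of a recent flare or its steroids can rank highly even if L-arginine does nothing

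*Combined protocol and SAP*

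**What the plan says.** The SAP section on baseline metabolites as predictors sets the groups: "We further defined the treatment response by reducing exacerbation events by 33% during L-arginine treatment". The individual change is computed as "events during treatment period minus events during placebo period)/events during placebo period". On who is left out: "Subjects with zero event at baseline or did not complete both treatment and placebo phase were excluded".

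The section on longitudinal metabolomic profiling lists three comparisons made with the MEBA time-series method. In the third, "treatment response vs. non-response groups during treatment period were tested using the method of multivariate empirical Bayes". The output is a ranking: "Hotelling-T2 statistics were used to rank the metabolites with different temporal profiles between two biological conditions under the study". No covariate is named, and no sample is set aside for being drawn near an exacerbation.

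Under Outcomes, events are counted over 12 weeks, and one route to an event is "need for initiation of oral steroids or an increased dose of inhaled corticoid steroid on any two consecutive days".

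The protocol's brief study outline schedules blood on Days 1, 80, 110 and 190, that is, at the start and near the end of each period. Day 1 includes "History and physical examination (brief) to verify stable clinical status". Day 80 lists only an updated clinical history.

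The predictor analysis is separate and uses pre-treatment blood: "The baseline metabolomic profiling (first visit) was used for the downstream analysis".

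**The concern.** The L-arginine period supplies both part of the group label and the on-treatment sample. A subject becomes a non-responder by having relatively many events in that period, and the sample is drawn after almost all of it has passed. Non-responders therefore reach that draw with more flares, and probably more steroid exposure, behind them. An untargeted panel may well contain metabolites that respond to inflammation or corticosteroids, and these would separate the groups whatever L-arginine does.

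Comparing with the start-of-period draw does not remove this, because the flare occurs after that draw and so enters the change. At stake is how the ranked list is read: a consequence of exacerbation or its treatment could be reported as a metabolic feature of response to L-arginine.

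**Working it through.** **The plan's own figure.** No figure is given for this contrast. The only sizing figure is 95% power for 0.6 SD in lung function. With 50 × 0.9 = 45 completers, noncentrality 0.6 × √45 = 4.02, 43 degrees of freedom and two-sided alpha 0.025, power is 95.2%. The figure reproduces, but has no bearing here beyond supplying 45 completers.

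**Inputs from the documents.** 45 completers; Poisson counts; 12-week periods; the 33% rule; end-of-period draws on Days 80 and 190.

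**Assumptions.** Mean events per period (2 to 3, with 1 and 4 as wider checks). A metabolite shift of 0.5 or 1 SD if a flare fell in the 14 or 28 days before the draw. Event rates either equal across persons or varying between them. The exclusion for zero events at baseline is read as zero placebo-period events, since that count is the denominator. A two-group t-test at 0.05 stands in for the MEBA ranking.

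**Method.** Both periods get the same event rate, so there is no drug effect. A subject is a responder if (placebo − L-arginine)/placebo ≥ 0.33. The spurious difference is then

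shift × (share of non-responders with a recent flare − share of responders with one).

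**Event imbalance with no drug effect.** Mean L-arginine-period events, responders versus non-responders, are 1.0 versus 2.8 at mean 2 and 1.6 versus 3.8 at mean 3.

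| Mean events, window, shift | Recent flare: responders vs non-responders | Difference | Positive at 0.05 |
|---|---|---|---|
| 3, 28 days, 1 SD | 43% vs 75% | 1 × 0.32 = 0.32 SD | 14–15% |
| 3, 28 days, 0.5 SD | 43% vs 75% | 0.5 × 0.32 = 0.16 SD | 7–8% |
| 2, 28 days, 1 SD | 30% vs 66% | 1 × 0.36 = 0.36 SD | 16% |
| 2, 14 days, 1 SD | 16% vs 40% | 1 × 0.24 = 0.24 SD | 10% |
| 2, 28 days, 1 SD, rates varying | 28% vs 71% | 1 × 0.43 = 0.43 SD | up to 19.5% |

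The last row's 19.5% is the highest single result; other runs with varying rates gave 16% to 18%. The weakest combination, 0.5 SD with a 14-day window at mean 2, gives 0.5 × 0.24 = 0.12 SD. With about 17 responders and 22 non-responders the noncentrality is 0.12 × √(17 × 22/39) = 0.37, a positive rate of roughly 6.6%.

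**Where the excess arises** (1 SD shift, means 1, 2 and 4, both windows):
- End-of-period draw: 7.3% to 19.5%.
- Start-to-end change: 7.5% to 17.5%.
- Pre-dose draw: 4.3% to 6.5%, close to nominal.
- End draw with no flare effect on the metabolite: 4.0% to 5.5%.
- End draw adjusted for recent flare: 4.1% to 6.1%.

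**Effect on ranking.** With 300 metabolites, 15% of them flare-sensitive by 1 SD, and mean 3, the flare-sensitive ones fill 33% of the top 10: about 3.3 places instead of 1.5.

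**Limits of adjustment.** The near-complete correction above uses the same indicator that generated the data. If a flare acts for 56 days but the indicator covers 28, about 0.15 SD remains and the error rate is 7.6%. If 10% of flare records are wrong, 0.13 SD and 6.7% remain. For a genuine on-treatment protective metabolite (assumed log-rate slope −0.5 per SD), adjustment cuts power from 87% to 63% at mean 3 and from 71% to 43% at mean 2.

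**Placebo-period contrast as a check.** At mean 3 (28 days, 1 SD) a flare-driven difference reverses to −0.17 SD on placebo, but a test detects it in only 7% to 8% of trials. With event rates varying between persons it shrinks to about −0.07 or −0.03 SD.

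**The case against.** The case on the other side has several parts.

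- **Purpose.** The SAP says this contrast ranks metabolites by temporal profile. It does not call them predictive or mechanistic; the predictive analysis is on first-visit blood. This stands. That the list would be read as marking response is an inference from the group labels, supported only by the protocol's general aim of defining mechanisms of benefit.
- **Direction of cause.** A reader might infer that cause and effect are simply reversed. The documents do not support that. A metabolite that L-arginine changes, and that prevents flares, would also differ between groups, and placebo-period events also enter the label. What is shown is possible reverse causation mixed with possible forward causation.
- **Clinical status is checked elsewhere.** Item 10 of Purpose and Procedures has investigators review exhaled NO and spirometry for signs of a flare, and Day 190 includes a full physical examination. This is correct, but it is a safety review. Nothing carries it into the analysis.
- **Visits.** The SAP mentions six study visits; the protocol outline gives one screening and four study visits. Any mid-period draws would reduce the overlap only in part.
- **Size.** The rates rest on assumptions, are modest in several settings, and come from t-tests on one draw, not from MEBA on a profile. This stands, and the bias needs at least some metabolites to respond to flares or steroids.
- **Exploratory status.** True, and it limits the weight of the point.

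**Conclusion.** The point holds as a limited flaw in one exploratory contrast. The overlap between label and sample follows from the SAP's own definitions, and no adjustment is described. For a flare-sensitive metabolite unrelated to L-arginine, the spurious difference is about 0.16 to 0.4 SD and the false-positive rate about 8% to 17%, against a nominal 5%. This assumes 2 to 3 events per period and a 0.5 to 1 SD shift from a flare in the last 14 to 28 days. The excess falls to roughly 6% to 7% when both shift and window are at the small end, and vanishes if flares do not alter the metabolite.

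A reader might go further and conclude that the search for response predictors is invalid, or that the trial's efficacy result is touched. Neither follows: the predictor analysis uses blood drawn before treatment, and the primary and secondary clinical analyses do not use this contrast. Nor do the documents justify discarding the contrast, since it may also carry real signal.

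**What to change.** Keep the third MEBA contrast. Beside it, report a linear mixed model for each metabolite with these terms:

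- response group;
- the pre-dose value of that period (Day 1 or Day 110);
- an indicator for an exacerbation or steroid escalation in the 28 days before the draw, repeated with a longer window.

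Take the indicator from the diary and clinical history. The outline describes the diary as covering symptoms and peak flow, so confirm that dates of steroid changes are available from the history or the event records.

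Describe metabolites whose group difference disappears after adjustment as possible consequences of exacerbation or its treatment, not as markers of L-arginine response. The placebo-period contrast may be shown descriptively, but not used as a pass/fail filter: it rarely detects the sign reversal, and a marker induced by L-arginine need not appear on placebo.

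The cost is SAP wording and one added analysis of a type the SAP already uses for metabolites; MEBA as described has no covariate term. The downside should be stated in the SAP: recent flare is part of the response label and may lie downstream of a true drug effect, so adjustment can remove real signal (the simulated fall in power from 87% to 63%). The adjusted result is therefore a companion to the contrast, not a replacement.
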